1.6.2 Phase 2 and Phase 3 Studies

In the psoriasis studies CC-10004-PSOR-001 and CC-10004-PSOR-004, apremilast treatment was associated with a decrease in dendritic cells and T-cells infiltrating the skin lesions within the epidermis and the dermis. In addition, a significant decrease in inducible nitric oxide synthase (iNOS) gene expression was observed in lesional skin biopsies taken 2, 4, or 12 weeks after treatment initiation. In Study CC-10004-PSOR-001, a decrease in the ability of whole blood to produce TNF- α in response to endotoxin was observed 2 hours after apremilast dosing. In Study CC-10004-PSOR-004, apremilast decreased lesional skin epidermal thickness and expression of

proinflammatory genes, including iNOS, IL-12/IL-23p40, IL-23p19, IL-17A, IL-22, and IL-8. In the PsA study CC-10004-PSA-002, apremilast treatment was associated with a decrease in IL-1 α , IL-6, IL-8, MCP-1, macrophage inflammatory protein-1 beta (MIP-1 β), TNF- α , matrix metalloproteinase protein-3 (MMP-3), ferritin, and a small increase in von Willebrand factor (vWF) plasma protein levels (note that vWF was within normal range [$< 120 \mu\text{g/mL}$]). Among these, the decrease in TNF- α and the increase in vWF were significantly associated with meeting the primary endpoint of the study (American College of Rheumatology [ACR] criteria for a 20% improvement [ACR 20] at Week 16). Taken together, these results suggest that partial inhibition of several pro-inflammatory mediators, including iNOS and TNF- α , may play a key role in the mechanism of action of apremilast in the treatment of psoriatic diseases.

In the AS study CC-10004-AS-001, 7 biomarkers had significant differences in percent change from baseline in one or more apremilast groups compared with placebo at more than one time point/analysis method combination: ferritin, intercellular adhesion molecule-1 (ICAM-1), IL-18, IL-8, MIP-1 β , osteoprotegerin (OPG), and sclerostin. Percent changes in both IL-8 and MIP-1 β were significantly associated with achievement of Assessment of SpondyloArthritis international Society (ASAS) 20 response in the APR 30 BID group.

Two multicenter randomized, double-blind, placebo controlled trials (PSOR-1 and PSOR -2) enrolled a total of 1257 subjects with moderate to severe plaque psoriasis [BSA $\geq 10\%$, static PGA ≥ 3 (mod to severe disease), PASI score ≥ 12 , candidates for phototherapy or systemic therapy]. In both studies, subjects were randomized 2:1 apremilast 30 mg BID or placebo for 16 weeks. Both studies assessed proportion of subjects achieving PASI-75 and proportion of subjects who achieved a sPGA of clear (0) or almost clear (1) at week 16. The mean PASI score pf 19.07 (median 16.80) and proportion of subjects with sPGA score of 3(moderate) or 4 (severe) at baseline were 70.0% and 29.8% respectively. The clinical response is as follows:

	PSOR-1 Placebo	PSOR-1 APR 30 mg BID	PSOR-2 Placebo	PSOR-2 APR 30 mg BID
N ^a	N=282	N=562	N=137	N=274
PASI ^b	15(5.3)	186 (33.1)	8 (5.8)	79 (28.8)
sPGA ^c clear/almost clear, n(%)	11 (3.9)	122 (21.7)	6 (4.4)	56 (20.4)

^a N is number of randomized and treated subjects

^b PASI=Psoriasis Area Severity Index

^c sPGA =Static Physician Global Assessment

1.6.3. Overall Safety

Apremilast is FDA approved for treatment of adult patients with active psoriatic arthritis and for the treatment of patients with moderate to severe plaque psoriasis who are candidates for phototherapy or systemic therapy.

In completed and ongoing apremilast Phase 2 or Phase 3 studies, the most commonly observed TEAEs (ie, those reported in > 5% of subjects) have been diarrhea, nausea, headache (including tension headache), upper respiratory tract infections, and nasopharyngitis. The majority of TEAEs of diarrhea, nausea, headache occurred within the first 2 weeks of treatment and most resolved within 4 weeks. The majority of reported TEAEs was mild or moderate in severity and resolved while subjects continued apremilast treatment. The incidence of SAEs was low and comparable between apremilast and placebo treatment groups in the placebo-controlled periods and was not driven by any single preferred term or any specific individual organ toxicity. The safety profile of apremilast is comparable in the psoriasis and PsA indications. The overall safety profile in subjects with AS, BD, and RA is similar to the safety profile in the psoriasis and PsA indications.

As of 30 Nov 2015, 19 deaths have been reported, including 18 deaths in Celgene-sponsored studies and 1 death in an IIT. There is no pattern indicating a causal relationship between death and apremilast treatment.

There was no evidence of an increased risk of major adverse cardiac events (MACE), malignancies, serious infections (including opportunistic infections) or suicidal behavior with apremilast treatment in clinical studies. There were 3 cases of small-vessel cutaneous vasculitis in subjects enrolled in clinical studies: 1 subject with PsA in the APR 30 BID treatment group and 2 subjects with RA (1 subject in the placebo group and 1 subject in the APR 30 BID group).

During a Phase 2 study (CC-10004-PSOR-003), proinflammatory biomarkers did not show evidence of vasculitis with apremilast treatment. Hypersensitivity, with 2 positive rechallenges, was confirmed in 1 subject with PsA in the APR 40 QD treatment group. Apremilast is contraindicated in subjects with known hypersensitivity to apremilast or its excipients. Observed weight loss was associated with apremilast treatment, without overt clinical consequences. A small number of laboratory abnormalities have been classified as adverse events (AEs) in completed and ongoing clinical studies. Most abnormal laboratory findings were not considered clinically significant, did not require medical intervention, and were self-limiting. There were no cases of liver function test (LFT) elevations meeting Hy's Law criteria (alanine aminotransferase [ALT] and/or aspartate aminotransferase [AST] > 3 × upper limit of normal [ULN] and bilirubin > 2 × ULN). No clinically significant differences between the placebo and apremilast treatment groups in vital signs or ECG findings have been observed in these studies.

Complete details of contraindications, precautions/warnings, and adverse reactions may be found in the package insert (**see attached**).

1.6.4. Worldwide Approval Status of Apremilast

Apremilast is marketed worldwide under the trade name Otezla®. Apremilast received its first global marketing approval from the Food and Drug Administration in the United States on 21 Mar 2014 for the treatment of adult patients with active PsA. Apremilast is

approved as a treatment for PsA and psoriasis. Apremilast is the first PDE4 inhibitor approved for the treatment of plaque psoriasis and PsA.

As of 30 Nov 2015, apremilast has been approved in 36 countries worldwide.

1.7. Study Rationale

There is no FDA-approved medication for chronic idiopathic pruritus (CIP). Apremilast has demonstrated notable activity and is approved for treatment in other pruritic inflammatory skin conditions such as psoriasis and is currently being investigated for atopic dermatitis. Additionally, we have preliminary data to suggest that apremilast's anti-inflammatory properties may work through its neuromodulatory effects by targeting neuronal cytokine pathways. The proposed study plans to assess the efficacy of apremilast 30 mg BID in the setting of CIP. A durable response to a medication is typically seen within one to two months of starting an efficacious medication in those who respond. Therefore, we have designed this study to end at Week 16 to definitively determine efficacy and conclude the study with confidence with regard to both efficacy and failure.

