Relapse	Increased findings of itch on history, physical examination, NRS itch score, and DLQI score following a defined clinical response
RNA-seq	RNA sequencing
SAE	Serious Adverse Event
sPGA	Static Physician Global Assessment
SUSAR	Suspected Unexpected Serious Adverse Reaction
TNF	Tumor Necrosis Factor
ULN	Upper Limit of Normal

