4. INVESTIGATIONAL PLAN

4.1. Overall Study Design

This study is an open label pilot study examining the efficacy of apremilast in the treatment of CIP. Ten (10) subjects who meet the eligibility criteria are planned to be enrolled. The total duration of subject participation will be 6 study visits over approximately 16 weeks. All subjects will receive apremilast 30 mg by mouth BID for 16 weeks.

All apremilast subjects will have visits at Screening, Baseline, and Weeks 2, 4, 8, 12, 16, and 18 (follow-up). Adverse events (AEs), medication history, clinical assessments, physical exam, and vital signs will be performed at each visit. Clinical safety laboratories will be performed at screening and Week 16 (EOT). All laboratory assessments will be performed using The Barnes-Jewish Hospital laboratory except for urine pregnancy tests (as applicable). NRS and DLQI scoring will be performed by a research nurse.

Two skin biopsies will be performed at the most pruritic site at Baseline and at Week 16 (adjacent to the initial biopsy site) for histopathological analysis and RNA-seq transcriptional analysis.

After the end-of-treatment visit (Week 16, or early termination), subjects will have follow-up assessments two weeks later (week 18) to monitor for durability of effect (relapse rate), AEs, medication history, vital signs, and clinical assessments.

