4.2. Measures Taken to Avoid Bias

This is an unblinded open label pilot study so the study will be biased for both the subject and the investigator.

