4.3. Number of Subjects

The study will include 10 subjects. Discontinued or drop-out subjects will not be replaced.

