5.1.2. Randomization and Blinding

There will be no randomization nor blinding in this study.

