7.6. Skin Biopsy Analysis: RNA Seq Analysis and Histology

Skin biopsy analysis will be used to investigate molecular signatures associated with response or resistance to treatment with the study drug. Ribonucleic acid (RNA) will be extracted from these samples to perform RNA-seq analysis that may include genome-wide gene expression profiling. The tissue will also be examined histopathologically.

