9.3. Level of Significance

We aim to reach statistical significance with our current design of a *P*-value of 0.05 or lower. If we do not, but observe a strong trend, we will perform power calculations to determine what level of enrollment would require the detection of a statistically significant effect.

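### Section 1.7 promises a definitive answer on efficacy and failure that a 10-subject, single-arm, open-label pilot cannot give; separately, 9.3 does not say which effect size its follow-on power calculation uses

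*Combined protocol and SAP*

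**What the plan says.** Section 1.7 (Study Rationale) argues that responders usually show a durable response within one to two months, and ends the study at Week 16 "to definitively determine efficacy and conclude the study with confidence with regard to both efficacy and failure".

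The design sections describe something more limited:

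- 4.1: "All subjects will receive apremilast 30 mg by mouth BID for 16 weeks".
- 5.1.2: "There will be no randomization nor blinding in this study".
- 4.2: "This is an unblinded open label pilot study so the study will be biased for both the subject and the investigator".
- 4.3: "The study will include 10 subjects. Discontinued or drop-out subjects will not be replaced".
- 9.2 and 9.4.1.2 name one test, a paired t-test of NRS at two time points. They mention further analyses of the interim visits without specifying them.
- 9.4.1.1.1 and 9.4.1.2.1 calculate change from baseline in NRS and DLQI at each visit.

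Section 9.3 aims for a P-value of 0.05 or lower, without stating sidedness, and continues: "If we do not, but observe a strong trend, we will perform power calculations to determine what level of enrollment would require the detection". It defines neither the trend nor the effect size to be used.

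Two other places rely on a response concept. The List of Abbreviations defines relapse as "Increased findings of itch on history, physical examination, NRS itch score, and DLQI score following a defined clinical response", and 7.6 looks for "molecular signatures associated with response or resistance to treatment with the study drug". No criterion for response or failure is given anywhere.

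**The concern.** A study that its own protocol calls biased cannot also be definitive on efficacy. Without a control arm, the paired test compares each subject with his or her own baseline. Expectation, natural course and regression to the mean (entry requires NRS of at least 7 at both Screening and Baseline) all contribute to the same mean change as any drug effect. More subjects or a smaller SD would not separate them.

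Failure is a second, different claim. A significance threshold says when a fall will be declared. It does not say what result would count as failure, and missing it does not show that the fall is negligible.

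What is at stake is the conclusion drawn at the end. The primary objective in 2.1.1 is worded as a demonstration, 9.3 aims for significance, and Section 9 plans no confidence interval to show how much remains uncertain. The 9.3 step bears on the next study: a sample size taken from a noisy observed effect can be badly wrong in either direction.

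**Working it through.** **The plan's own figure.** N = 10 cannot be reproduced. Section 9.2 gives no target effect, power or SD of change. Its SD of 1.1 (mean 8.8) describes single scores in 10 clinic patients, not changes.

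**Inputs.** From the documents: n = 10, significance level 0.05, paired t-test. Assumed: two-sided testing; SD of change 1.1, 1.56 (1.1 × √2, which is equal SDs and zero correlation), 2.0, 2.4 and 3.0; an illustrative modest fall of 1.5 points and a large fall of 3 points.

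**Formulas.** Half-width of the 95% confidence interval = t(0.975, n−1) × SD/√n, with t = 2.262 at n = 10. Power comes from the noncentral t distribution with n−1 degrees of freedom and noncentrality (fall/SD) × √n. Miss rate = 1 − power.

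Example at SD 2.0: half-width = 2.262 × 2.0/3.162 = 1.43. Noncentrality for 1.5 points = 0.75 × 3.162 = 2.37, which gives a miss rate of 0.438.

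| SD of change (assumed) | CI half-width | 1.5-point fall missed, two-sided | 1.5-point fall missed, one-sided | Power for 3-point fall, two-sided |
|---|---|---|---|---|
| 1.1 | 0.79 | 3% | 1% | >99.9% |
| 1.56 | 1.11 | 23% | 12% | >99.9% |
| 2.0 | 1.43 | 44% | 29% | 98.7% |
| 2.4 | 1.72 | 58% | 43% | 93.9% |
| 3.0 | 2.15 | 71% | 57% | 80.3% |

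**Drop-outs.** They are not replaced (4.3). With an assumed 8 completers (t = 2.365), the half-width runs from 0.92 to 2.51, the two-sided miss rate for 1.5 points from 9% to 77%, and power for 3 points at SD 3.0 falls to 68%.

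**Section 9.3, only if the observed effect is used.** At n = 10 the observed standardised effect is d = t/√10, so the P-value alone fixes d, and d fixes the N needed for 80% power:

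| Two-sided P | t (9 df) | d | Required N |
|---|---|---|---|
| 0.05 | 2.262 | 0.715 | 18 |
| 0.10 | 1.833 | 0.580 | 26 |
| 0.15 | 1.574 | 0.498 | 34 |
| 0.20 | 1.383 | 0.437 | 43 |

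True effects of 0.2, 0.6 and 1.0 SD need N of 199, 24 and 10. In simulation (1,000,000 trials each), the mean observed effect among trials with two-sided P between 0.05 and 0.20 was 0.56, 0.58 and 0.60 SD respectively. Within that band the observed effect barely distinguishes the three cases. The band is an assumption, since 9.3 does not define a trend.

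**How well the pilot gives the SD of change.** The 95% limits are the estimate times √((n−1)/χ²). With 10 completers: √(9/19.023) = 0.69 to √(9/2.700) = 1.83. With 8: √(7/16.013) = 0.66 to √(7/1.690) = 2.04. Both assume normal changes.

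**The case against.** The best reply is that 1.7 is narrative. Its sentence justifies the length of treatment, no rule in Section 9 draws on it, the document calls itself a pilot, 4.2 admits bias openly, and the objective is improvement from baseline rather than superiority to a control. Much of this stands: the duration argument is sound as far as it goes, and the harm lies in how results may be described, not in a faulty test. But the admission in 4.2 is the reason 1.7 cannot keep its wording, and the demonstration language in 2.1.1 points the same way.

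A reader might go further in four directions that the documents do not support:

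- *Ten subjects are too few to learn anything about failure.* A 3-point mean fall has at least 80% power at every assumed SD with 10 completers, so large effects are likely to be detected. The weakness concerns modest falls, larger SDs or fewer completers.
- *The Week 18 data go unanalysed.* Sections 9.4.1.1.1 and 9.4.1.2.1 calculate change from baseline at each visit, and Week 18 is a listed visit for both scores. What is missing is a test or a relapse analysis. Being open-label, that visit would not repair attribution in any case.
- *Section 9.3 will use the observed effect.* It names no effect size, so the N figures above are conditional.
- *Section 9.3 plans to add subjects to this study and retest.* It does not say whether the enrolment is for an extension or a new study. Planning a later study from a pilot is ordinary practice.

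**Conclusion.** The concern holds in limited form. That the design cannot attribute a fall to apremilast follows from the protocol's own text and needs no numerical assumption. That it cannot settle failure holds for modest effects: the chance of missing a 1.5-point fall is 3% to 71%, depending on an SD of change that the documents do not give. Both the SDs and the 1.5 points are illustrative, and one-sided testing would lower the range to 1% to 57%. The 0.05 target in 9.3 is a significance threshold and does not serve as a failure criterion.

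The 9.3 point is separate and narrower: the effect size is left open, and one natural choice would make the calculation uninformative. Neither point calls for a change to the duration, the visits, the test or N. This is worth correcting, but it does not prevent the study from doing what a pilot can do.

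**What to change.** 1. **Section 1.7.** Keep the Week 16 rationale. Delete the word definitively and the claim of confidence about efficacy and failure. Add, for example: *As an open-label pilot, this study will estimate the mean within-subject change in NRS itch score with a 95% confidence interval; it will not by itself establish efficacy or failure.* Reword the primary objective in the Synopsis and 2.1.1 to estimating change from Baseline, and amend the first sentence of 9.3 to match, so that the three places agree.

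2. **Section 9.4.1.2 and Synopsis, Statistical Methods.** Report the mean change from Baseline with its 95% confidence interval alongside the paired t-test, at the primary time point. That time point must first be reconciled: 2.2.1 says Week 16 and 9.4.1.1.1 says Week 12.

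3. **Section 9.3, second sentence.** Replace with, for example: *Any later study will be sized on a clinically relevant difference fixed in advance and on the SD of change seen here, allowing for its uncertainty given the number of completers, and not on the observed effect.* Do not write the SD multipliers into the protocol, because they depend on how many subjects complete.

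Cost: text edits and one interval computed from data already collected. The downside is a weaker stated claim.

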1.8. Potential Risks and Benefits of the Treatment Regimen

As of 20 Sep 2015 the worldwide exposure to commercial apremilast was approximately 41,244 patients. The safety profile of apremilast in the postmarketing setting remains similar to that observed in the registrational clinical program. The most frequently reported adverse events have been gastrointestinal (diarrhea, nausea, vomiting, abdominal discomfort) and nervous system disorders (headache). There have been no changes required to the Company Core Data Sheet (CCDS) based on postmarketing safety data.

The safety profile of apremilast is comparable in the psoriasis and PsA indications. The most commonly observed TEAEs (ie, those reported in > 5% of subjects) have been diarrhea, nausea, headache (including tension headache), upper respiratory tract infections, and nasopharyngitis.

The majority of the TEAEs of diarrhea, nausea, and headache occurred within the first 2 weeks of treatment, and most resolved within 4 weeks. The majority of reported TEAEs were mild or moderate in severity and resolved while subjects continued apremilast treatment. The incidence of SAEs was low and comparable between apremilast and placebo treatment groups in the placebo-controlled periods and was not driven by any single preferred term or any specific individual organ toxicity. The overall safety profile in the AS, BD, and RA indications is similar to the safety profile in the psoriasis and PsA indications.

The proposed Apremilast 30 mg BID regimen, if successful, will provide an effective therapy for CIP and improve the quality of life in subjects with CIP, a highly debilitating chronic pruritic disorder.

2. STUDY OBJECTIVES AND ENDPOINTS

2.1. Study Objective(s)

2.1.1. Primary Objective

- To demonstrate that apremilast 30 mg taken orally twice daily (BID) results in improvement in Numerical Rating Scale (NRS) itch score from Baseline.

2.1.2. Secondary Objective

Key Secondary objectives:

- To demonstrate that apremilast 30 mg taken orally twice daily (BID) results in improvement in Dermatology Life Quality Index (DLQI) from Baseline.

2.1.3. Exploratory Objective

- To identify whether skin transcriptomic signatures are altered in response to treatment with apremilast by RNA sequencing (RNA-seq).

2.2. Study Endpoints

2.2.1. Primary Endpoint

- Absolute change in Numerical Rating Scale (NRS) itch score from Baseline to Week 16. The NRS itch score will be recalled from the prior 24 hours first and then the prior 1 week.

2.2.2. Secondary Endpoint(s)

Key secondary endpoints:

- Absolute change in Dermatology Life Quality Index (DLQI) from Baseline to week 16.

Other secondary endpoints:

- Numerical Rating Scale (NRS) itch score at Screening, Baseline, Weeks 2, 4, 8, 12, 16, and 18.
- Dermatology Life Quality Index (DLQI) at Screening, Baseline, Weeks 2, 4, 8, 12, 16, and 18.

- AEs; performing physical examinations; collecting vital signs; and collecting laboratory data for hematology, and serum chemistry.

2.2.3. Exploratory Endpoint(s)

- Skin RNA-seq analysis at Baseline (Week 0) and Week 16.

3. SUBJECT ELIGIBILITY

Deviations from eligibility criteria are not allowed because they can potentially jeopardize the scientific integrity of the study, regulatory acceptability, and/or subject safety. Therefore, adherence to the criteria as specified in the Protocol is essential.

3.1. Subject Inclusion Criteria

A subject who meets all of the following criteria may be included in the study:

1. Male and non-pregnant, non-lactating female subjects aged 18 years or older, in good general health (except for disease under study) as judged by the Investigator, based on medical history, PE, clinical laboratories and urinalysis, and absence of uncontrolled significant co-morbidities.
2. Diagnosed with chronic idiopathic pruritus (CIP) with a NRS Itch Score of ≥ 7 at both Screening and Baseline.
3. Diagnosis of CIP for at least 6 weeks prior to screening.
4. Willingness to avoid pregnancy or fathering of children based on the criteria below:
 - a. Woman of nonchildbearing potential (surgically sterile with a hysterectomy and/or bilateral oophorectomy OR postmenopausal, defined by last menstrual period for at least 24 months before screening).
 - b. Woman of childbearing potential who has a negative serum pregnancy test at screening and a negative urine pregnancy test at baseline and who agrees to take appropriate precautions to avoid pregnancy (with at least 99% certainty) from screening through safety follow-up. Permitted methods that are at least 99% effective in preventing pregnancy (see Appendix A) should be communicated to the subject and their understanding confirmed. Chosen form of contraception must be effective by the time female subject is randomized.
 - c. Man who agrees to take appropriate precautions to avoid fathering children (with at least 99% certainty) from screening through safety follow-up. Permitted methods that are at least 99% effective in preventing pregnancy (see Appendix A) should be communicated to the subject and their understanding confirmed.
5. Ability and willingness to provide written informed consent.
6. Willing and able to comply with all study requirements and restrictions.

7. Willing to not participate in any other interventional trial for the duration of their participation.
8. Subjects must be in good health as determined by past medical history, physical examination, electrocardiogram, clinical laboratory tests and vital signs.
9. Failure of a course 2-week course of treatment with topical triamcinolone 0.1% ointment BID.
10. Histopathological demonstration of dermal edema, skin eosinophils, mast cell activation or lymphocytic infiltration.

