6. STUDY ASSESSMENTS

All study assessments will be performed as indicated in the schedule of assessments **Table 1**, in the order listed, and all laboratory assessments will be performed as indicated in **Table 2**:

Table 1: Schedule of Assessments

Evaluation	Screening	Treatment						Follow-Up
	Day -28 to -1	Baseline	Week 2 Day 14 \pm 3 Days	Week 4 Day 28 \pm 3 Days	Week 8 Day 56 \pm 3 Days	Week 12 Day 84 \pm 3 Days	Week 16 Day 112 \pm 3 Days	Week 18 Day 96 \pm 3 Days
Clinic visit	X	X	X	X	X	X	X	X
Informed consent	X							
Inclusion/exclusion criteria	X	X						
Demography and medical history	X							
Prior/concomitant medications	X	X	X	X	X	X	X	X
Height and body weight	X							
Comprehensive physical exam	X							
Targeted physical exam (if indicated)		X	X	X	X	X	X	X
Vital signs and weight	X	X	X	X	X	X	X	X
Laboratory assessments	X						X	
Chest x-ray	X							
Hepatitis screening tests	X							
Pregnancy test ^a	X	X	X	X	X	X	X	X
Efficacy assessment (NRS itch score)	X	X	X	X	X	X	X	X
Derm Quality of Life Index	X	X	X	X	X	X	X	X
Study drug dispensed/Collect study drug bottles		X	X	X	X	X	X	
Assess compliance			X	X	X	X	X	
Skin biopsy RNA-seq transcriptional profile, and Histopathological analysis		X					X	
Assess AEs	X	X	X	X	X	X	X	X

^aAll women will have a serum pregnancy test conducted at the screening visit and urine pregnancy tests conducted at all other visits (including baseline) unless postmenopausal (defined as >12 months from last menstrual period) or surgically sterile)

Table 2: Clinical Laboratory Assessments

Serum Chemistries	Hematology
Albumin Alkaline phosphatase ALT AST Bicarbonate Blood urea nitrogen Calcium Chloride Creatinine Glucose Phosphorus Potassium Sodium Total bilirubin Total serum protein	Hematocrit Hemoglobin Mean corpuscular volume Platelet count Red blood cell count Reticulocyte count White blood cell count White blood cell differential (5 part): 
 • Basophils • Eosinophils • Lymphocytes • Monocytes • Neutrophils
Other	Serology
ESR Lactate dehydrogenase Urinalysis Urine pregnancy test (at site) Serum pregnancy test TSH	Hepatitis B surface antigen Hepatitis C virus antibody HIV p25 antigen

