7.4.5.3. Pregnancy Testing

Pregnancy testing will be performed on all female subjects as noted in the schedules of assessments in **Table 1**. Serum pregnancy test will be obtained at screening. A urine pregnancy test will be obtained all other visits. A positive urine pregnancy test should be confirmed by a serum pregnancy test.

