APPENDIX A. CONTRACEPTIVE METHOD INFORMATION

For Subjects Participating in the Study:

The risks to a fetus or to a nursing child from apremilast are not known at this time. Results of the animal and in vitro studies can be found in the IB. All females of childbearing potential (FCBP) must use one of the approved contraceptive options while on investigational product and for at least 28 days after administration of the last dose of the investigational product. The following methods that can achieve a failure rate of less than 1% per year when used consistently and correctly are considered as highly effective birth control methods.

Such methods include:

- Combined (estrogen and progestogen containing) hormonal contraception associated with inhibition of ovulation¹
 - oral
 - intravaginal
 - transdermal
- Progestogen-only hormonal contraception associated with inhibition of ovulation¹
 - oral
 - injectable
 - implantable²
- Intrauterine device (IUD)²
- Intrauterine hormone-releasing system (IUS)²
- Bilateral tubal occlusion²
- Vasectomised partner^{2,3}
- Sexual abstinence⁴

Male subjects (including those who have had a vasectomy) who engage in activity in which conception is possible must use barrier contraception (male latex condom or nonlatex condom NOT made out of natural [animal] membrane [for example, polyurethane]) while on investigational product and for at least 28 days after the last dose of investigational product.

¹ Hormonal contraception may be susceptible to interaction with the IMP, which may reduce the efficacy of the contraception method.

² Contraception methods that in the context of this guidance are considered to have low user dependency.

³ Vasectomised partner is a highly effective method provided of avoiding pregnancy that partner is the sole sexual partner of the WOCBP trial participant and that the vasectomised partner has received medical assessment of the surgical success.

⁴ In the context of this guidance, sexual abstinence is considered a highly effective method only if defined as refraining from heterosexual intercourse during the entire period of risk associated with the study treatments. The reliability of sexual abstinence needs to be evaluated in relation to the duration of the clinical trial and the preferred and usual lifestyle of the subject.

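### Table 1 footnote a waives pregnancy tests from 12 months after the last period, but inclusion 4a requires 24 months, so on-treatment testing is unclear for women in between

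*Combined protocol and SAP*

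**What the plan says.** Section 3.1 sorts women into two groups. Inclusion 4a covers nonchildbearing potential: a woman is either "surgically sterile with a hysterectomy and/or bilateral oophorectomy" or "postmenopausal, defined by last menstrual period for at least 24 months before screening". Any other woman must enter under 4b, which requires effective contraception together with "a negative serum pregnancy test at screening and a negative urine pregnancy test at baseline". Section 3 adds: "Deviations from eligibility criteria are not allowed".

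Table 1 footnote a sets a serum test at screening and urine tests at every other visit, baseline included, "unless postmenopausal (defined as >12 months from last menstrual period) or surgically sterile". It names no surgical procedure and no date from which the 12 months are counted back.

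Section 7.4.5.3 points both ways. It first says "Pregnancy testing will be performed on all female subjects as noted in the schedules of assessments", which leads back to Table 1 and its footnote. It then says "A urine pregnancy test will be obtained all other visits", with no exemption.

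Appendix A states that the risk to a fetus is not known. Section 8.3 stops study drug at once on a pregnancy, a suspected pregnancy or a positive test.

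**The concern.** The protocol uses two cut-offs for the same clinical status. The looser one sits in the schedule of assessments, which site staff work from at each visit. A woman whom the protocol regards as able to conceive, and therefore obliges to use contraception, can be exempt from testing on the page that tells staff what to do.

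What is at stake is detection of an unsuspected pregnancy on treatment. The stop rule in Section 8.3 needs something to trigger it. A woman who has had no period for more than a year has no missed period to raise suspicion, so for her a scheduled test is the most likely trigger. The NRS and DLQI analyses and the sample size are not touched.

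**Working it through.** No statistical figure is involved. The check is a comparison of the texts followed by a count of visits.

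**Step 1. Who falls between the rules.** For a woman who is not surgically sterile:

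| Time since last period | Inclusion 4a/4b | Footnote a | Agreement |
|---|---|---|---|
| 12 months or less | childbearing potential (4b) | tested | yes |
| more than 12, less than 24 months | childbearing potential (4b) | exempt | no |
| 24 months or more before screening | nonchildbearing potential (4a) | exempt | yes |

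The discrepancy is a band 24 − 12 = 12 months wide.

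**Step 2. How many tests are scheduled (Table 1).** One serum test at screening plus 7 urine tests (baseline, Weeks 2, 4, 8, 12, 16 and 18): 1 + 7 = 8.

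**Step 3. Which of them are safe.** The screening serum test and the baseline urine test are conditions of entry under 4b, and Section 3 permits no departure from entry criteria. The footnote cannot remove them without making the woman ineligible. That leaves 8 − 2 = 6 tests on which the texts disagree.

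**Step 4. Which of the 6 could shorten exposure.** Treatment ends at Week 16, so a positive result can stop drug early only at Weeks 2, 4, 8 and 12: 4 tests.

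**Step 5. Time on drug without a scheduled test.** Taking baseline as Day 0 (assumption; Table 1 gives no day number for it), the planned test days through end of treatment are 0, 14, 28, 56, 84 and 112.
- Unqualified sentence of 7.4.5.3 followed: gaps of 14, 14, 28, 28 and 28 days. The longest is 28 days, or 28 + 3 + 3 = 34 days at the extremes of the visit windows.
- Footnote followed: no scheduled test after baseline. Treatment then runs untested for about 112 days, or 112 − 3 = 109 to 112 + 3 = 115 days with the window. The Week 16 and Week 18 tests are waived too, so this is time from baseline to end of treatment and not an interval that a later test closes.

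**Step 6. Which text governs.** Section 6 says assessments are performed as Table 1 indicates, and Section 7.4.5 refers to Table 1 for the tests required at each visit. Both favour the footnote. The unqualified sentence in 7.4.5.3 favours testing. No order of precedence is given, so the number of lost tests is 0 or up to 6 per affected woman, depending on the reading.

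**The case against.** The strongest reply is that the protocol already protects these women. Inclusion 4b demands two negative entry tests and contraception of at least 99% effectiveness, Section 7.4.5.3 contains an unqualified instruction to test at all other visits, and Section 8.3 stops drug on suspicion alone. With 10 subjects, the number of women in the 12-to-24-month band is probably small. It could be added that 12 months is itself a sensible definition of menopause.

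Most of this stands, and it limits the size of the point. It does not remove the conflict: contraception and a suspicion rule do not replace the repeat tests, and the unqualified sentence sits next to one that defers to the footnote. Nor does it matter here which cut-off is medically better, since one protocol cannot apply both to the same women.

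Stronger readings that a reader might infer are not supported:
- *Women able to conceive could properly enter untested.* The footnote's wording reaches the baseline test, and perhaps the screening test, but 4b and Section 3 still require both.
- *On-treatment testing is absent for these women.* The texts are inconsistent. On one reading every test is done.
- *Surgical sterility is undefined, so women with tubal occlusion are exempt.* The footnote does not define the term, but 4a does, and carrying that definition over is the ordinary reading. Appendix A lists "Bilateral tubal occlusion" as a contraceptive method. This group is missed only if staff misread the footnote.

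**Conclusion.** The conflict is real, and nothing in the document resolves it. It is a minor internal inconsistency with a bearing on patient safety and none on efficacy.

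Its size per affected woman lies between two bounds. If staff follow the unqualified sentence in 7.4.5.3, 0 tests are lost. If they follow the footnote, up to 6 post-entry urine tests are lost, including 4 that could have stopped drug early, and about 112 days of treatment pass with no scheduled test after baseline.

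This rests on the entry tests being done as 4b requires and on the planned visit days in Table 1. The documents do not give the number of affected women or any probability of pregnancy, so no expected number of missed pregnancies can be stated. The mismatch of 12 against 24 months is certain. The loss of tests is conditional on which text staff follow.

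**What to change.** In Table 1 footnote a, replace the present exemption with: *except women of nonchildbearing potential as defined in inclusion 4a*. This brings across both the 24-month rule, counted from screening, and the list of procedures that count as surgical sterility. Put the same exception in Section 7.4.5.3, so that its sentence on all other visits agrees with the footnote. Every woman who must use contraception under 4b is then also tested at every visit.

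The cost is two wording edits and at most 6 additional urine tests per affected woman, all at visits already scheduled. No visits are added.
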